We use Chi squared test to explore the association between weight change and dichotomous outcomes (dose reduction in treatment). Then separate regression models are used to further estimate the association as multivariate analyses. Weight change will be analysed as continuous variable, and ordinal variable (coding continuously 0, 1 and 2 for weight loss, stable weight and weight gain respectively). Dose reduction is analysed as dichotomous variable. The models will be adjusted for age, sex, targeted therapies. Other variables, such as Charlson's comorbidity index, and BMI can be included as covariables. Likelihood ratio test

will be used to compare models for selecting the final model. BMI has been found to be correlated positively with muscle mass, and is associated with treatment outcomes and side effects in different cancers.

Stata is used for all analyses. All significance tests are two-sided.

e) Existing Facilities:

The Department of Clinical Oncology at Tuen Mun Hospital will be the primary center for the conduct and analytic work in this study. We have an experienced team of researchers of performing cancer research.

f) Justification of Requirements:

Travel costs: We have included in our budget travelling costs for one trip to attend international conferences (\$10,000) in year 3. This is to reflect the need to present results at leading international conferences. This travel is mainly intended for international conference attendance.

Publication costs: These will cover the fee to publish the results in high-profile impact Open Access journals estimated at \$20,000 each. We will promote Open Access publications, according to the 2003 Berlin Declaration, as an additional mean to disseminate research effectively to large audiences. Publications will be uploaded to the open access repository "Dryad" and official site of Tuen Mun Hospital.

Other goods: scientific software: i) Stata-SE 15 one-core statistical software license for 1 computer (USD\$1,695 ~ HKD\$13,302). English editing services for research articles estimated at \$5,000 each. We further prepare \$3,000 for reference materials. We budget \$1,000 each year for stationeries and other expenses (e.g. printing and postage) because we expect printing and photocopying of a large amount of literature as well as miscellaneous office expenses relate mostly to the data collection, analysis, reporting and writing phase of the study.

g) Purpose and Potential:

CRC ranks the first in cancer incidence and second in cancer-related mortality in Hong Kong; and around 60% of CRC patients develop metastasis during their course of illness. This study will quantify the impact of weight change on the tolerability of treatment, as reflected by the need of dose reduction, and prognosis. Weight is easy and cheap to measure, which is suitable for resource-tight healthcare system such as that in Hong Kong. These are clinically important end-points which potentially impact the treatment strategies of stage IV colorectal cancer, including the nutritional intervention, and early stop or reducing dose of chemotherapy in case of weight loss.

Based on this study, further research can be conducted to evaluate the health economics on different treatment strategies which may affect the funding decision of health care payer and the future health care policy.

[figure not shown]
The results of this study will be submitted to international, peer-reviewed journals, and be presented in academic conferences.

h) Key References:

1. Hong Kong Cancer Registry. Hong Kong Special Administration Region. 2017 [Available from: <http://www3.ha.org.hk/cancereg/>].
6. Network NCC. NCCN Clinical Practice Guidelines in Oncology. Colon cancer. version 1. 2018 ed.

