Study Protocol

Change in Body Weight During Treatment of Advanced Colorectal Cancer

PROTOCOL DATE: January 1, 2019

PROPOSED RESEARCH PROJECT

- a) Title:
Change in Body Weight During Treatment of Advanced Colorectal Cancer

Abstract

Objectives: To evaluate whether change in body weight in advanced colorectal cancer patients occurring during systemic anti-cancer treatment influences treatment outcomes

Hypothesis to be tested: Weight loss during treatment is associated with adverse treatment outcomes in patients with advanced colorectal cancer, compared to patients without weight loss or with weight gain.

Design: A pilot, prospective, single-centered observational study of patients with advanced colorectal cancer having first line systemic anti-cancer treatment.

Setting: Outpatient Clinical Oncology clinic in Tuen Mun Hospital

Participants: Patients having histologically proven stage IV colorectal adenocarcinoma, requiring systemic anti-cancer treatment, which entail chemotherapy (5-fluouracil, capecitabine, oxaliplatin and irinotecan) with or without targeted therapy (cetuximab or bevacizumab) as first line treatment.

Main outcome measures: Primary outcomes: disease control rate, progression free survival. Secondary outcomes: Dose reduction of systemic chemotherapy.

- b) Introduction:

Colorectal cancer (CRC) is a significant and growing health burden in Hong Kong. According to data from Hong Kong Cancer Registry, CRC ranked the first in incidence and the second in mortality, with around 5,000 new cases diagnosed and more than 2,000 cancer-related mortality in 2014.¹ Around one-fourth of CRC present as metastatic disease; it is also estimated that 50-60% of patients diagnosed with CRC eventually develop metastasis during their course of disease.² Among metastatic CRC (mCRC) patients, only few with limited metastases are potential long-term survivors after receiving locoregional treatment,³ while the majority of them are incurable and the standard treatment is systemic therapy.

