(1) Primary endpoint: DCR which includes stable disease, partial response and complete response as defined in RECIST 1.1; and PFS defined as the time from randomization until first evidence of objective tumour progression (as defined in RECIST 1.1) or death from any cause, with censoring of patients who are lost to follow-up.

(2) Secondary endpoints: Dose reduction is defined as <70% of relative dose intensity, which represents the ratio of dose intensity (dose given per unit body surface area per unit time i.e. mg/m²/week) actually administered, to standard dose intensity.⁸

d) Plan of Investigation:

(i) Subjects

Sample size calculation:

We used power analysis program G*Power to calculate sample size.²⁴ Estimated proportion of subjects having significant weight loss is approximately 15%. Risk ratio of dose reduction was about 3.0 for patients with significant weight loss, according to a study in adjuvant setting. Prior study indicated that the failure rate among controls is 0.2. We will need to recruit 240 patients to be able to reject the null hypothesis that the primary endpoints (incidence of dose reduction) for patient with and without significant weight loss are equal with probability (power) 0.8. Assuming 10% loss to follow-up, total number of patients to require is 264. The Type I error probability associated with this test of this null hypothesis is 0.05. We will use logistic regression to evaluate this null hypothesis.

Inclusion criteria for studies

We recruit male and female patients aged 18 years or older with stage IV, histologically

confirmed colorectal adenocarcinoma who will receive systemic treatment, an Eastern Cooperative Oncology Group (ECOG) performance status of 0–2, an estimated life expectancy of greater than 3 months, and adequate organ function. We exclude patients who are pregnant, have human immunodeficiency virus infection and acquired immune deficiency syndrome (HIV/AIDS), and past medical history of another cancer.

(ii) Methods

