This study is prospective observational cohort study, recruitment period is 24 months. We start to collect data once patient is recruited and individual data can be available before end of recruitment period. Baseline weight (in kilogram), height (in centimeter), and BMI (in kilogram per height in meters squared) are measured by medical assistants closest to the start of treatment as baseline, and at onset of every treatment cycle. Patients are weighed without shoes, in light clothes or hospital gowns, using a Seca digital scale with graduation 0.01 kg. Body height is measured to the nearest 0.1 cm with the same digital scale with graduation 0.1 cm.

Patients' demographics (age, sex, and ethnicity), and disease characteristics (left versus right colon cancer, RAS status) are collected. Other clinical variables considered to be important prognostic factors are collected and included in the analysis: TNM cancer stage, histological grade, peripheral blood neutrophil-lymphocyte ratio, serum carcinoembryonic antigen (CEA) level, ECOG performance status, Charlson comorbidity index.²⁵

(iii) Study design

Disease is staged by CT from thorax to pelvis or positron emission tomography-computed tomography (PET-CT). Clinical assessment (history taking and physical examination) and routine laboratory tests (complete blood counts, liver and renal function tests) are performed at baseline and before every treatment cycle according to daily practice. Adverse events are assessed using clinical and laboratory data, and graded by using Common Terminology Criteria for Adverse Effects, version 4.02.

The treatment doses and administration dates are recorded at chemotherapy infusion tables. Any treatment delay and dose reduction is recorded.

Patient is followed up at each treatment cycle. Some patients opt for treatment interruption after four to six months of treatment to avoid cumulative toxicity and preserve a good quality of life, and are put on close monitoring, treatment can be reinitiated when progression is detected. Interval assessments of disease response are made with physical examination (every clinic visit), serum CEA level, and three to six monthly CT, PET-CT or X-ray.

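### The dose-reduction comparison ignores time on treatment, so it mixes tolerance with treatment duration and can be biased in either direction

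*Protocol*

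**What the plan says.** All references are to the protocol.

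- **Outcome** (main outcome measures, secondary endpoints): "Dose reduction is defined as <70% of relative dose intensity". RDI is the delivered dose per square metre per week divided by the standard dose intensity. The text does not say whether the weeks are those actually spent on treatment or those of a planned course.
- **Analysis** (data processing and analysis, secondary outcomes): "We use Chi squared test to explore the association between weight change and dichotomous outcomes (dose reduction in treatment", then regression. "Dose reduction is analysed as dichotomous variable". The sample size section names the model for the same outcome: "We will use logistic regression to evaluate this null hypothesis". Adjustment is for age, sex and targeted therapies, with the Charlson index and BMI as options. Neither cycles nor time on treatment is listed, and nothing is said about treatment ended by progression or death.
- **Exposure** (same section): the maximum weight change during treatment, grouped at 5% loss and 5% gain, and also used as a continuous variable.
- **Treatment length** (study design): "Some patients opt for treatment interruption after four to six months of treatment to avoid cumulative toxicity".
- **Data** (methods and study design): weight is measured at the start of every cycle, and "The treatment doses and administration dates are recorded at chemotherapy infusion tables".

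**The concern.** Dose reduction is the protocol's measure of treatment tolerance and the only endpoint with a sample-size calculation. The abstract's hypothesis is: "Weight loss during treatment is associated with adverse treatment outcomes in patients with advanced colorectal cancer". Progression-free survival (PFS) is one of those outcomes. If the hypothesis is true, weight-loss patients tend to have fewer cycles in which tolerance can be observed. The exposure pulls the other way, because a patient treated for longer has more weighings at which a loss above 5% can appear.

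A two-by-two table of maximum weight change against RDI below 70% cannot separate these effects from a real link between weight loss and tolerance. The stated purpose of the study includes informing early stopping or dose reduction when weight falls, so a spurious association, or a spurious absence of one, would matter.

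**Working it through.** **The plan's own figures.** The plan gives no figure for this bias. From its sample size section I take 15% with weight loss and 20% dose reduction among controls. The stated 240 does not come out of those inputs: about 79 patients suffice for a risk ratio of 3.0, and about 230 are needed if 3.0 is read as an odds ratio. That is a separate matter and does not bear on this point.

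**Assumptions (none is in the protocol).** Constant monthly rates, median PFS 9 months without weight loss, at most 9 months on first-line treatment, and no effect of weight loss on tolerance. So h = ln 2 / 9 = 0.0770 per month.

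**Step 1. Weight loss as a baseline group, outcome as a first occurrence.** The chance of an event at rate d before treatment ends is

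P = d/(d+h) × (1 − exp(−9(d+h))).

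- Setting P = 0.20 for controls gives d = 0.0353.
- PFS hazard ratio 1.5 (h = 0.1155): 0.0353/0.1508 × (1 − exp(−1.358)) = 0.234 × 0.743 = 0.174. Risk ratio 0.87.
- PFS hazard ratio 2.0 (h = 0.1540): 0.0353/0.1893 × (1 − exp(−1.704)) = 0.187 × 0.818 = 0.153. Risk ratio 0.76.

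Here shorter treatment makes weight loss look protective.

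**Step 2. Same model, but weight loss also occurs during treatment.** Let weight loss arise at rate w, independent of dose reduction and without effect on PFS. For a total rate s, the chance of no event is

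E(s) = h/(h+s) × (1 − exp(−9(h+s))) + exp(−9(h+s)).

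- 1 − E(w) = 0.15 gives w = 0.0255; d = 0.0353 as before.
- E(w+d) = 0.5587 × (1 − 0.2892) + 0.2892 = 0.6863.
- P(both) = 0.15 + 0.20 − 1 + 0.6863 = 0.0363.
- Dose reduction with weight loss: 0.0363/0.15 = 0.242. Without: (0.20 − 0.0363)/0.85 = 0.193. Risk ratio 1.26.

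The two are linked only because both need time on treatment. In simulation, letting weight loss raise the PFS hazard afterwards gives 1.19, 1.15 and 1.06 at PFS hazard ratios of 1.5, 2 and 3. The ratio shrinks but stays above 1.

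**Step 3. The protocol's actual outcome, RDI below 70%.** Dividing by weeks does not equalise the opportunity to cross the threshold. Suppose, purely as arithmetic, that a patient receives full dose for 4 cycles and half dose after that. Over n cycles actually given, RDI = (4 + 0.5(n − 4))/n, which is below 0.70 only when n exceeds 10. If progression ends treatment at cycle 6, RDI is 5/6 = 83% and the patient counts as not reduced. Against a planned 12-cycle course, even 6 full-dose cycles give 6/12 = 50%, and the patient counts as reduced.

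Simulated risk ratios with no true effect on tolerance:

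| Exposure and RDI time base | PFS hazard ratio | Risk ratio |
|---|---|---|
| Baseline group, actual weeks, dose falls after toxicity onset | 1.5; 2.0 | 0.86; 0.77 |
| Baseline group, actual weeks, constant dose per cycle* | 1.5 to 3 | 1.04 to 1.11 |
| Baseline group, planned 12-cycle course* | 1.5 to 3 | 1.11 to 1.79 |
| Weight loss arising during treatment, RDI below 70% | 1 to 2 | 1.15 to 1.25 |

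*Median PFS of 10 months assumed.

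**Step 4. What an analysis per time at risk recovers.** With a true rate ratio of 2.5, classifying each patient once for the whole course gives only 1.55 to 1.67. Letting weight-loss status change when the loss occurs gives about 2.5. Adding time at risk alone is therefore not enough; the exposure must be time-updated as well.

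**The case against.** The strongest reply is that RDI is already a rate. A patient with three cycles has an RDI and can be below 70%, and one early delay weighs more in a short course. That is correct: it would be wrong to say that early progressors cannot be counted, and with a constant dose per cycle the distortion is small (1.04 to 1.11). It does not remove the problem when doses fall over the course or when the exposure builds up with time.

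The protocol's mention of cumulative toxicity explains why some patients take a break. It does not state that RDI declines with cycles, so that remains an assumption.

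This is a secondary endpoint of a pilot study, and a statistical analysis plan not seen here may define the RDI time base. The dichotomous comparison and its covariates, however, are fixed in the protocol itself.

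A reader might infer two stronger things:

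- **That the association is pulled towards or below no effect whenever weight loss shortens PFS.** The documents do not support this. It needs weight loss to be a baseline group, and the protocol defines it as maximum change during treatment, for which the illustrations stay above 1. A planned-course RDI also reverses the direction.
- **That the study loses much of its power.** This depends on the effect chosen. Calibrated to the protocol's risk ratio of 3.0 at equal PFS, the Step 1 type of model keeps power at 99.8%, 98% and 93% for PFS hazard ratios of 1, 1.5 and 2.

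**Conclusion.** The planned dose-reduction estimate mixes tolerance with treatment duration, and its bias can go either way. With no true effect, the illustrations run from about 0.77 to 0.86 (baseline weight-loss group, actual weeks, PFS hazard ratio 2.0 to 1.5) to about 1.15 to 1.25 (the protocol's maximum-change exposure, PFS hazard ratio 1 to 2), and lie above 1 with a planned-course RDI. Under the exposure as written, the likelier error is that weight loss looks harmful to tolerance when it is not.

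The missing time element and the exposure definition are read directly from the protocol. The sizes rest on assumed PFS, toxicity and weight-loss rates and show only that the distortion can be material. No claim about lost power is made. The analysis should be changed before the data are analysed.

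**What to change.** 1. State that RDI is computed over actual weeks on first-line treatment, and say how the weeks of an elective break count.
2. Make the main dose-reduction analysis the time from first dose to cumulative RDI below 70%, by cause-specific Cox regression. Enter weight change from baseline as a covariate updated at each cycle, with the planned adjustment variables. End time at risk at progression, death or the end of first-line treatment.
3. Keep the chi-squared table and the end-of-treatment proportion below 70% as description.
4. Add a sensitivity analysis that starts after the first few cycles, because a running RDI is unstable early and a single delay could trigger the event.
5. Let the sample-size sentence name the test it refers to.

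**Cost.** Changes of wording, plus somewhat more programming. Doses, dates and weights per cycle are already recorded. A hazard ratio replaces a simple difference in proportions, which is harder to explain; the descriptive table partly makes up for that.
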